### 5.3 Lost to Follow-Up

Reasonable number of attempts (at least three attempts on three different days) to contact the subject (including written correspondence and phone calls) should be done and documented in the source documents by the site. When the Investigator or designee(s) declare(s) a subject is lost to follow-up, the lost to follow-up date will be recorded. The date of lost to follow up corresponds to the date of the end of study of the subject.

If the investigational site has lost track of the subject but the subject has reached the maximum number of study days (70 days), then the Investigator or designee(s) will declare the subject lost to follow-up at this date.

### 5.4 Violation of Selection Criteria

Any subjects who do not meet the entry criteria after signing the ICF and prior to Enrollment at Admission will be considered as screen failures and will be replaced by other subjects. Re-screening of subjects will not be permitted.

Any violation of selection criteria detected after enrollment have to be reported within 24 hours after awareness to the Clinical Research Associate (Monitor).

## 6 INVESTIGATIONAL PRODUCTS

### 6.1 Description of Investigational Products

#### 6.1.1 Investigational Products

P3P is a novel type of nicotine-containing product (NCP) which generates an inhalable aerosol from nicotine-containing powder when air is drawn through it. P3P does not contain tobacco and does not require heating and/or electronics for its operation.

It is a single use product which has two components that perform different functions:

- A consumable component, which comprises a tube-shaped body and a capsule containing the P3P powder. Once the capsule is activated, i.e. pierced with an accessory component, the user is able to draw on the consumable so that airflow passes through the consumable and releases the powder from the capsule.
- An accessory component, which is a mechanical unit with a needle to pierce the capsule that enables the release of the powder from the capsule. Each capsule should be pierced immediately before product use.

The P3P powder is composed of a nicotine-containing powder mixed with menthol flavor particles. The nicotine-containing powder has a particle size that allows deep lung deposition whereas the flavor particles have a larger particle size and deposit in the oropharyngeal cavity. One P3P product contains 1 (P3P-1mg) or 2 mg (P3P-2mg) of nicotine.

P3P will be provided by the Sponsor and its distribution by site will be controlled by a qualified and appropriately trained designee as specified in the IP handling manual.

#### 6.1.2 Packaging and Labeling

Five P3P consumables will be packed in a pouch. Four pouches (or 20 Consumables) and one accessory will be packed in a pack. Six packs will be packed in a carton. Each carton/pack/pouch will be labelled with the necessary information according to local regulatory requirements, and blinding requirements. The contents of each label will be specified in the IP handling manual.

### 6.2 Use of Investigational Products

Subjects can use up to 15 P3P products daily during the exposure period, except during the PK assessments and wash-out hours preceding those assessments, as described below. Subjects will never be forced to use P3P and will be free to stop using P3P at any time during the study.

### 6.2.1 Admission (Day -1 – V2)

After enrollment, subjects will be required to perform product test by using up to 6 P3P products (alternating between P3P-1mg and P3P-2mg). In order to continue in the study, each subject will need to test at least one product of each P3P variant during the product test. Product test must be performed after the subjects have abstained from the use of any tobacco/nicotine containing products for at least 4 hours (4h wash-out period prior to product test). The product test period should be organized in a dedicated supervised area (i.e. not a dedicated cigarette smoking area). Subjects will be instructed on how to activate and use P3Pas specified in the P3P user guide. . They will be asked to puff with sufficient intensity to trigger the spinning of the capsule. The subject should hear the sound of the capsule spin and/or feel the vibration of the product induced by the spinning. Product test should end at least 10 hours prior to the start of product use for PK assessment on Day 1 (section [6.2.2](#))

After the product test, subjects not willing and/or unable to use P3P will be discontinued from the study and will enter a 14-day Safety Follow-Up Period.

At Day -1, after check-in on site, subjects will not be allowed to smoke cigarettes and/or use any other tobacco/nicotine containing products with the exception of P3P which can only be used during the product test period.

### 6.2.2 Product use during confinement (V2, V6)

During the investigational period subjects will be requested to attend two on-site visits with overnight stays (with a confinement of 3-days at V2 and 2-days at V6). At the beginning of these visits, subjects will be asked to give their cigarettes and used/unused P3P products to the site staff.

Smoking cigarettes and/or use any tobacco/nicotine containing products other than P3P will not be allowed on site during the visits. On the first day of V6 (Day 29), subjects will be allowed to use P3P until the evening which will be subsequently followed by a wash-out period of at least 10 hours prior to the PK assessments which will be done on the second day of the visits. P3P use on the first day of V2 will only be allowed during the product test period (section [6.2.1](#)). P3P will be dispensed by the site staff on a product by product basis during the timeframe allowed by the protocol. The distribution should be recorded at site logs by site staff and the use of any product during the confinement days should be also recorded in the product use diary which is completed by the subject. The time of the use of the last tobacco/nicotine containing product, prior to the start of the wash-out period should be recorded.

In the morning of the second day of V2 (Day 1) and V6 (Day 30), following at least 10 hours of abstinence from any tobacco and nicotine containing products, subjects will use a single P3P product with no restrictions on the number of puffs or puffing frequency (*ad libitum* use) for a duration of up to 15 minutes. The start of product use (first puff) will be considered as  $T_0$ . The start and stop time of product use will be recorded. At V2 (Day 1), after the end of the blood sampling for PK assessments (4h after  $T_0$ ) subjects will be allowed to restart the use of

#### Confidentiality Statement

Data and information contained in this document are considered to constitute trade secrets and confidential commercial information, and the legal protections provided to such trade secrets and confidential information are hereby claimed under the provisions of applicable law. No part of this document may be publicly disclosed without the written consent of Philip Morris Products S.A.

P3P. Subjects will remain on-site until the evening of Day 2 and will be allowed to use up to 15 P3P products/day on Day 1 and Day 2. During this time, subjects will not be allowed to smoke cigarettes and/or use any other tobacco/nicotine containing products with the exception of P3P.

#### 6.2.3 Ambulatory Exposure Period (Discharge at V2 until start of V6)

Subjects will be instructed to use P3P exclusively (using up to 15 products daily) from discharge at V2 until check-in at V6. Use of cigarettes and/or other tobacco and nicotine containing products during the ambulatory Exposure Period will not be a reason for discontinuing a subject from the study, but should be avoided as much as possible. During the entire exposure period, subjects will report their daily consumption in a product use diary (section 7.8.1)

#### 6.2.4 Safety Follow-Up Period

Use of the investigational product will not be permitted during the Safety Follow-Up Period. Subjects will be allowed to use their own cigarettes.

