### 8.2.2 Period of Collection

AEs (including SAEs) will be collected from the time of ICF signature until the EOS.

Any AEs which occur during the screening period will be captured by the study site staff and assessed by the Investigator or designee(s) in order to establish relationship to study procedures.

During a 14-day Safety Follow-Up Period new AEs/SAEs will be recorded and ongoing AEs/SAEs will be followed-up by the study site. In general, AEs will be followed-up until resolved, stabilized (i.e., no worsening of the event), or a plausible explanation for the event has been found and until the end of the study. At the end of the Safety Follow-Up all subjects will be contacted via phone in order to check the status of the ongoing AEs and also to collect any new AEs/SAEs experienced by the subjects. Subjects should be contacted 14-days after Day 30. In case they cannot be reached two additional attempts at the next 2 consecutive days will be made. If the subjects cannot be reached after the three attempts they will be declared

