4 ABBREVIATIONS AND DEFINITION OF TERMS

The following abbreviations are used within this SAP.

ABOUT	Assessment of behavioral outcomes related to tobacco and nicotine products
AE	Adverse event
ANOVA	Analysis of variance
ANCOVA	Analysis of covariance
ATC	Anatomical Therapeutic and Chemical
AUC	Area under the concentration-time curve
AUC _(0-4h)	Partial AUC, assessed between 0 and 4 hours post P3P use
BLOQ	Below the Lower limit of Quantification
BMI	Body mass index
BoExp	Biomarker of exposure
CEMA	2-cyanoethylmercapturic acid
CI	Confidence interval
C _{max}	Maximum concentration
COT	Cotinine
CRF	Case report form
CRO	Contract research organization
CTCAE	Common terminology criteria for adverse events and common toxicity criteria
CTMS	Clinical trial management system
CV	Coefficient of variation
CYP2A6	Cytochrome P450 2A6
DDE	Drug Dictionary Enhanced
ECG	Electrocardiogram
eCRF	Electronic Case Report Form
EOS	End of study
FEV ₁	Forced expiratory volume in 1 second
FVC	Forced vital capacity
HCOT	Trans-3'hydroxycotinine
HIV	Human immunodeficiency virus
HnB	Heat not Burn
HPHCs	Harmful and potentially harmful constituents
ICF	Informed consent form
ICH	International Conference on Harmonization
LLOQ	Lower limit of quantification
MedDRA	Medical dictionary for regulatory activities
PK	Pharmacokinetic(s)
PMPSA	Philip Morris Products S.A.
PT	Preferred Term
QTcB	QT Interval Corrected using Bazett's Formula

QTcF	QT Interval Corrected using Fridericia's Formula
RSR	Research Study Report
SAE	Serious adverse event
SAP	Statistical analysis plan
SD	Standard Deviation
SOC	System Organ Class
T	Time point
T ₀	Time point of start of product use
t _{max}	Time to maximum concentration
TFL	Tables, Figures, and Listings
Total NNAL	Total 4-(Methylnitrosamino)-1-(3-pyridyl)-1-butanol
ULOQ	Upper limit of quantification
VAS	Visual analogue scale
WBC	White blood cell (count)
WHO	World Health Organization
λ _z	Terminal elimination rate constant

The following special terms are used in this SAP:

Screen failure	Subject who signs the ICF but is not enrolled at Admission.
Enrollment	On Admission Visit (Day -1) for eligible subjects after all applicable inclusion and exclusion criteria have been satisfactorily assessed and met.
First product use time point	Start of the product test use.
Randomization	Allocation of the respective product, P3P-1mg or P3P-2mg, after product test on Day -1.

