12.5.9.1 Safety Reporting

An exposure emergent AE is defined as an AE that occurs after first product use or that is present prior to first product use and becomes more severe after first product use. All other AEs will not be summarized but provided in listings only.

Any AEs which occur after ICF signature will be captured by the site collaborators and assessed by the Investigator or designee in order to establish relationship or relatedness in respect to study procedures. The AE listings will include all AEs captured in the database at any time during the study (including those from subjects who were not in the safety population). All AEs occurring after the product test use will be included in the summary tables. During the screening period prior to the first product use, only study procedure related AEs will be listed.

AEs reported from enrolled subjects, but who did not start use on day 1 or later will be summarized in a separate listing: “Enrolled but not started randomized product use AEs”. Furthermore AEs reported after discharge on Day 30 are summarized in a separate listing ‘Safety follow-up AEs’.

If there are more than 10 AEs, the tables will also be split by product exposure period. The product exposure periods will be defined as below

Partial dates will not be imputed, but assumptions will be made as follows to assign to exposure-emergent or not:

Date information	Assign as
Partial date, e.g., --May2012, or ----2011. If month/year is the same as, or later than the month and/or year of first product use	Exposure-emergent
Partial date, e.g., --May2012, or ----2011. If month and/or year is earlier than the month and/or year of first product use	Not exposure-emergent

If exposure emergent adverse events cannot be attributed to P3P due to e.g. missing start time, the worst case principle will be applied : i.e. the event will be allocated to P3P use.

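### AEs that start in the 14-day off-product follow-up are pooled with exposure-period AEs in the by-variant tables, because the SAP sets no end to exposure emergence

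*Protocol*

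**What the plan says.** **What happens in follow-up.** Protocol 6.2.4: "Use of the investigational product will not be permitted during the Safety Follow-Up Period. Subjects will be allowed to use their own cigarettes". Under protocol 5.2, subjects who stop early enter the same 14 days.

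**How long AEs are collected.** Protocol 8.2.2: "AEs (including SAEs) will be collected from the time of ICF signature until the EOS". The end of study (EOS) includes the follow-up.

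**What counts as exposure emergent.** SAP 12.5.9.1: "An exposure emergent AE is defined as an AE that occurs after first product use", or one already present that worsens after that point. SAP section 4 sets first product use at the Day -1 product test: "Start of the product test use". No end date or lag is given.

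**What goes in the tables.** SAP 12.5.9.1: "All AEs occurring after the product test use will be included in the summary tables". SAP 12.5.9.2 and 12.5.9.2.1 present these tables by variant and overall.

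**What is shown separately.** SAP 12.5.9.1 provides Listing 15.1.23.3 for AEs reported after Day 30 discharge. It also splits the tables by product exposure period, but only if there are more than 10 AEs. The period definitions announced there do not follow. Table 7 in SAP 7.9 has the product test, Day 1, Day 2 and four periods ending at V6, and an overall exposure period of Day 1 to Day 29.

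**The concern.** Protocol 12.6.3 makes AE data the primary assessment of safety, and two of the AE tables (15.2.23.1 and 15.2.23.2) are topline outputs. A reader of an exposure-emergent column headed P3P-1mg or P3P-2mg will take it as experience on that variant. As specified, the column also holds events that began after P3P was withdrawn and own cigarettes were allowed again. Nothing in the table shows how many there are.

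The two devices that might separate them fall short. The period split is conditional and has no category for a follow-up onset. The listing takes nothing out of the tables and, as worded, does not clearly reach follow-up AEs of subjects who stopped before Day 30.

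**Working it through.** The plan gives no figure to reproduce: the sample size of 60 is empirical and no AE rate is stated. The check is therefore the text, the length of the counted window, and the direction of the effect.

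**1. Does any rule remove a follow-up AE from the tables?** Take a completer with an AE starting 5 days after Day 30 discharge.
- It is collected, because collection runs to EOS.
- It is exposure emergent, because it occurs after the product test and there is no upper limit.
- It enters the summary tables under the randomized variant.
- It also appears in Listing 15.1.23.3, but no sentence makes that listing a substitute for the tables.
- If the period split is triggered, the AE fits none of the Table 7 periods.

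**2. How much of the window is off product?** Inputs: Day -1 (1 day), Day 1 to Day 30 (30 days), follow-up (14 days).
- Counted window = 1 + 30 + 14 = 45 days, of which 31 have P3P access.
- Off-product share = 14/45 = 31%.
- With the V6 window of ±2 days: 14/(29 + 14) = 33% to 14/(33 + 14) = 30%.

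**3. Can this be turned into incidence?** Only by assumption. Suppose 20% of subjects have an AE over the 31 days, at constant hazard λ = -ln(0.8)/31 per day. Let the follow-up hazard be k times λ. Incidence over the full window is 1 - exp(-λ(31 + 14k)):
- k = 0.25: 22.0%
- k = 1: 27.7%
- k = 2: 34.6%

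The documents fix neither the 20% nor k, so this range only shows that the answer is open.

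**4. What happens to the comparison of variants?** Let m1 and m2 be the expected AEs per subject in the exposure period and b the expected number in follow-up, the same in both arms. The difference is (m2 + b) - (m1 + b) = m2 - m1, so it does not change. The ratio (m2 + b)/(m1 + b) moves toward 1. For the share of subjects with at least one AE, if a fraction q of subjects in each arm has no follow-up AE, independently of earlier AEs, the difference becomes q(p2 - p1), which is somewhat smaller. No between-variant test of AEs is planned.

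**The case against.** **Counting to EOS is legitimate.** Secondary objective 4 concerns safety and tolerability during the study, and the study includes follow-up. Counting through follow-up is a common conservative choice: it keeps late-onset events and withdrawal symptoms, which protocol 2.3.3 lists as foreseeable, in the main count. This stands, and it is why the window should not simply be cut at discharge. A cut at last P3P use would also differ from one at discharge, since subjects who quit all products stay in the study without P3P (protocol 2.3.1).

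**Other outputs help.** Table 15.2.23.3 gives product-related AEs, and Listing 15.1.23.3 sits beside the exposure-emergent listing as if the two were distinct. If the period split is triggered and Table 7 applies, its columns would leave follow-up onsets out. All this softens the problem. But relatedness is a judgement rather than an onset date, the split depends on the AE count, and the SAP never says whether the listing replaces table entry.

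**Follow-up is observed differently.** AEs are collected mainly by face-to-face interview. Exposure has confinement, weekly visits and scheduled tests, while follow-up has one scheduled phone call to all subjects at its end. A 31% share of days is therefore not a 31% share of events. This stands.

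**Stronger readings the documents do not support.**
- A reader might infer a fixed number of percentage points of inflation. That needs AE rates the documents do not give, and equal ascertainment on and off product.
- A reader might infer that subjects who decline after the product test, with 14/15 = 93% of their counted days off product, distort both arms. They are never randomized. Under SAP 12.1.3 they can enter only the overall figures.
- A reader might infer a clean contrast between P3P time and smoking time. Follow-up smoking is permitted, not certain, and protocol 6.2.3 does not discontinue subjects for cigarette use during ambulatory exposure.

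**Conclusion.** The point holds as a gap in SAP 12.5.9.1 and Table 7; protocol 6.2.4 itself contains no error. Read literally, the SAP pools AEs that begin in the 14-day follow-up with exposure-period AEs in every by-variant AE and SAE table. For a completer, 31% of the counted days (30% to 33% with the visit window) are off product, assuming attendance as scheduled and the full 14 days of follow-up.

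The effect on incidence is unknown. It falls mainly on the absolute incidence shown for each variant. A reader might infer that the comparison of 2 mg with 1 mg is biased. With equal follow-up in both arms, the expected difference in event counts is unchanged; only ratios and the difference in the share of subjects affected are compressed, in tables that are descriptive.

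This is an inexpensive improvement to a secondary, descriptive analysis. It does not touch the primary PK objective.

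**What to change.** 1. Keep the count of all AEs from the product test to EOS as the overall figure.
2. Add a Safety Follow-Up period to Table 7, running from Day 30 discharge or early termination to EOS.
3. In Tables 15.2.23.x and 15.2.24.x, show AEs and SAEs by onset in separate exposure-period and follow-up columns, by variant and overall. Do this whatever the number of AEs, so that it does not depend on the more-than-10 rule.
4. State that Listing 15.1.23.3 is additional to the tables and includes the follow-up AEs of early terminators.

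The cost is a few lines of SAP text and one extra column set in the AE and SAE shells. No new data are needed, no event leaves the overall count, and SAP section 3 allows amendment before database lock. The new columns separate study periods, not strictly time on and off P3P, and a table footnote should say so.

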#### 6.2.5 Stopping Rules for Investigational Product

For safety purposes, use of P3P should be temporarily reduced (decreasing number or/and intensity of puffs) or stopped in the event of any signs suggesting nicotine overexposure, e.g., gastrointestinal disturbance (nausea, vomiting, diarrhea, stomach or abdominal pain), cold sweats, headache, dizziness and breathing problems, or any other reasons at the discretion of the Investigator. Signs suggesting respiratory disturbance (e.g., wheezing, dyspnoea, chest tightness) which may be related to P3P powder inhalation could also be taken in consideration for P3P reduced use or P3P stopping.

#### 6.2.6 Stopping Rules for the Study

The study may be stopped if the subjects are placed at risk because of clinically significant findings or SAEs that, for example:

- are assessed as causally related to P3P
- are not considered to be consistent with continuation of the study
- are not consistent with the information provided in Section 6.5 of the current P3P Investigator's Brochure.

The Sponsor, Investigator, and/or Ethics Committee(s) reserve the right to terminate or suspend the study at any time; however this should be discussed between the relevant parties beforehand and the reason for such decision recorded. Should this occur, all data available will also be recorded in the case report forms (CRFs).

---

#### Confidentiality Statement

Data and information contained in this document are considered to constitute trade secrets and confidential commercial information, and the legal protections provided to such trade secrets and confidential information are hereby claimed under the provisions of applicable law. No part of this document may be publicly disclosed without the written consent of Philip Morris Products S.A.

---

The Investigator should notify the EC in writing of the study's completion or early termination. In the event that the study is terminated early, every effort should be made by the Investigator, investigational site personnel, and Sponsor to follow AEs and SAEs for all subjects until the end of the 14-Day Safety Follow-Up Period.

### **6.3 Method for Assigning Subjects to Product Variant**

At Day -1 after product test subjects who confirmed their willingness to continue in the study will be randomized using an interactive web response system (IWRS). Subjects will be randomized to one of the two arms: P3P-1mg or P3P-2mg in a 1:1 ratio.

Each randomization group (P3P-1mg, P3P-2mg) will be stratified on sex distribution to ensure that at least 40% of each sex is randomized in each group.

